4.4 Analysis of secondary outcomes

To evaluate the effect of CBZ on height, bone conformation, pain, and health related quality of life in children with MCDS over 12 months.

4.4.1 Descriptive and graphical analysis

Outcome measures:

- 1) Height, for age and sex, zscore
- 2) Bone age SD age related zscore (taken from the left wrist x-ray)
- 3) Tanner and Whitehouse bone age (TW3)
- 4) Femoral neck-shaft angle (NSA) on left and right legs
- 5) Deviation from midline at knee
- *6)* PedsQL Pain Coping Inventory total score by participant (both parent and child completed if available) *[Average score of 41 questions 0, 1 or 2 for each question]*
- Pediatric Pain Questionnaire: VAS scores for the questions "how you feel now" and "worst pain you had this week" (both parent and child completed if available) converted to a score of 0 (no pain) to 100 (Severe pain)
- 8) Paediatric Quality of Life Inventory (PedsQL) total score

[Likert scale used to score each of 15 questions transformed to a 0-100 scale as follows: 0=100, 1=75, 2=50, 3=25, 4=0]

- 9) PedsQL Psychosocial Health sub-domain score
- 10) PedsQL Physical Health sub-domain score

will be plotted by individual for each available visit, indicating visits which took place during the baseline observation period and during the treatment phase.

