11.2.2 Analysis of Secondary Outcome Measures

The SAP will provide full details of the analysis of clinical secondary outcomes.

Responses to the EQ-5D-Y descriptive components will be reported in tabular form and responses will be converted into health state utilities using the recommended scoring algorithm available at the time of trial analysis for the UK. Currently, this is the scoring system for the UK general population. Changes in health related quality of life, based on responses to the EQ-5D-Y, will be compared across time points.

Responses to the PEDSQOL will be converted into scores using the recommended method. Scores will be reported for the Psychosocial Health and Physical Health sub-domains as well as the total score.

Use of surgical interventions to manage the condition will be captured on the eCRF over the whole follow up period. These will be reported descriptively as the type and proportion of participants experiencing an event per three month period from baseline until the end of trial follow up.

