2.3 Randomisation and blinding

There is no randomisation or blinding in this trial.

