2.4.1.2 Secondary objectives/endpoints

	Objective	Outcome		
Secondary	To evaluate the effect of CBZ on height in children with MCDS over 12 months	Alteration from baseline in height percentile over 12 months		
	To evaluate the effect of CBZ on bone conformation in children with MCDS over 12 months	Alteration from baseline in long bone alignment and configuration over 12 month as measured by X-ray analysis		
To evaluate the effect of CBZ on pain in children with MCDS over 12 monthsAlteration from over 12 months• PEDSQL Pa • PEDSQL Pa		 Alteration from baseline in pain perception over 12 months as measured by: PEDSQL Pain Coping Inventory PEDSQL Pain Questionnaire 		

To evaluate the effect of CBZ on health related quality of life of children with MCDS	Alteration from baseline in HRQOL scores over 12 months as measured by:		scores over			
over 12 months	•	Paediatric (PedsQL) EQ-5D-Y	Quality	of	Life	Inventory

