4.4.2 Statistical modelling

A more general version of the statistical model used for the analysis of the primary outcome will be used to assess changes in secondary outcome measures possibly related to treatment. The model additionally allows for a possible step change in response at the start of the treatment period.

Defining τ_{ij} , t_{ij} and T_i in the same manner as used for the primary outcome analysis, let y_{ij} denote a continuous response variable, the model for which is:

$$y_{ij} = \beta_1 + \beta_2 t_{ij} + \beta_3 \tau_{ij} (t_{ij} - T_i) + \beta_4 \tau_{ij} + \varepsilon_{ij},$$

where β_1 , β_2 , β_3 and β_4 are regression parameters to be estimated using Generalised Estimating Equations (GEE). The "working" correlation matrix is the same as used for the primary analysis.

- During the baseline period, $y_{ij} = \beta_1 + \beta_2 t_{ij} + \varepsilon_{ij}$.
- At the start of the treatment period, $y_{ij} = \beta_1 + \beta_2 T_i + \beta_4 + \varepsilon_{ij}$.
- During the treatment period, $y_{ij} = (\beta_1 \beta_3 T_i + \beta_4) + (\beta_2 + \beta_3)t_{ij} + \varepsilon_{ij}$.

The step change in response at the start of the treatment period is modelled by the parameter β_4 ; the parameter β_3 represents the increase in slope during the treatment period compared to the baseline period as previously.

Height *zscore*, PedsQL Pain Coping Inventory total score, Pediatric Pain Questionnaire VAS score, Paediatric Quality of Life Inventory (PedsQL) total score, PedsQL Psychosocial Health sub-domain score and PedsQL Physical Health sub-domain score will be analysed using the STATA commend **xtgee** to estimate the parameters of the regression model above. The parameter β_3 and β_4 will be reported together with 95% confidence interval. The Huber/White/sandwich estimator of variance will be used to obtain confidence intervals [in STATA: vce(robust)].

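### The bone-conformation objective gets plots but no estimate, the SAP contains no EQ-5D-Y analysis, and the modelled secondary outcomes lack a 12-month contrast

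*SAP*

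**What the plan says.** SAP 4.4 states the aim: "To evaluate the effect of CBZ on height, bone conformation, pain, and health related quality of life in children with MCDS over 12 months". For bone, SAP 2.4.1.2 defines the endpoint as "Alteration from baseline in long bone alignment and configuration over 12 month as measured by X-ray analysis".

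SAP 4.4.1 lists ten outcomes. Four come from the X-rays: bone-age z-score, TW3 bone age, "Femoral neck-shaft angle (NSA) on left and right legs", and deviation from the midline at the knee. The only instruction for the list is that its items "will be plotted by individual for each available visit".

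SAP 4.4.2 then gives a GEE model with a slope change (β3) and a step at the start of treatment (β4). It names six outcomes, ending with "PedsQL Psychosocial Health sub-domain score and PedsQL Physical Health sub-domain score will be analysed using the STATA commend". No bone measure is among the six. β3 and β4 are to be reported with 95% intervals.

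EQ-5D-Y is a quality-of-life endpoint in SAP 2.4.1.2 but appears in neither list, and the SAP gives no scoring for it. Protocol 11.2.2 plans tables and conversion to utilities, and says: "Changes in health related quality of life, based on responses to the EQ-5D-Y, will be compared across time points". The same section leaves the detail for clinical secondary outcomes to the SAP. Protocol 12 refers to a separate health economics analysis plan for the decision model.

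**The concern.** Protocol 2.3 says that growth, bone alignment and quality of life will inform whether a randomised trial is planned. Children have repeated X-rays for this purpose. If the SAP is followed as written, the report will contain individual bone plots with no mean change and no interval, and nothing on EQ-5D-Y.

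For the modelled outcomes the endpoint is a 12-month alteration, but the output is two separate parameters. As a hypothetical example, a step of +6 points and a slope change of −8 points per year put the 12-month value 2 points below the projected baseline trend. A reader shown +6 and −8 has no interval for that −2.

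Timing adds to this. SAP version 1.0 is dated 8 February 2024, after the last-visit limit of 31 January 2024. In an open, single-arm trial, an estimate chosen after the plots have been seen would be post hoc.

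**Working it through.** **1. Matching endpoints to analyses**

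| Objective | Measures | Plotted (4.4.1) | Modelled (4.4.2) |
|---|---|---|---|
| Height | z-score | yes | yes |
| Bone | neck-shaft angle, knee deviation | yes | no |
| Bone | bone-age z-score, TW3 | yes | no |
| Pain | coping total, pain VAS | yes | yes |
| Quality of life | PedsQL total, psychosocial, physical | yes | yes |
| Quality of life | EQ-5D-Y | no | no |

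Plotted: 1 + 4 + 2 + 3 = 10. Modelled: 1 + 2 + 3 = 6. The four missing items are exactly the bone measures. Two of them measure alignment and two measure skeletal maturation. SAP 2.4.1.2.2 still carries question marks against TW3.

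**2. What the 4.4.2 model implies at 12 months**

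One year into treatment (t = T + 1) the modelled mean is β1 + β2(T + 1) + β3 + β4. The projected baseline line is β1 + β2(T + 1).

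- Departure from the baseline trend: β4 + β3 × 1 year.
- Change from the pre-treatment level β1 + β2T: β2 + β3 + β4. β2 is not listed for reporting.
- Var(β4 + β3) = Var(β3) + Var(β4) + 2Cov(β3, β4). The covariance is not listed either.

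**3. Size of the covariance effect**

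The plan gives no SD, correlation or target precision to reproduce; N = 40 was set by feasibility. Assumptions: 11 Stage 1 and 29 Stage 2 children, complete data, the first 12 treatment months, the last baseline visit and the first treatment visit counted separately, outcome SD = 1, and exchangeable correlation ρ.

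On the 3-monthly questionnaire schedule at ρ = 0.5, SE(β3) = 0.254, SE(β4) = 0.134 and their correlation is 0.14.

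- With covariance: √(0.0645 + 0.0180 + 2 × 0.14 × 0.254 × 0.134) = √0.0920 = 0.303.
- Without covariance: √0.0825 = 0.287.

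At ρ = 0.5, 0.7 and 0.9, SE(β4 + β3) is 0.303, 0.241 and 0.142 SD, with 95% half-widths of 0.59, 0.47 and 0.28 SD.

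**4. Can the same model serve the bone measures?**

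Protocol Tables 8 and 9 schedule Stage 2 films at visit 1, visit 2.1, and 6 and 12 months of treatment. SAP 4.4.2 writes the start of treatment with β4 included, so visit 2.1 would be coded as treatment. For Stage 2 (T = 0.5 year):

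| Film | time | time on treatment | step |
|---|---|---|---|
| Visit 1 | 0 | 0 | 0 |
| Visit 2.1 | 0.5 | 0 | 1 |
| 6 months | 1.0 | 0.5 | 1 |
| 12 months | 1.5 | 1.0 | 1 |

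In every row, time = 0.5 × step + time on treatment. The design therefore has rank 3 for 4 parameters, and within children the baseline slope rests on the 11 Stage 1 participants. If Stage 1 visits 3 and 1.1 coincide, as the schedule allows, and the single film is coded as treatment, the same identity holds there with 1 in place of 0.5. If visit 2.1 is coded as baseline, the Stage 2 rank is 4.

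The paired change from the start-of-treatment film to 12 months has SE = √(2(1 − ρ)/40): 0.158, 0.122 and 0.071 SD. Multiplying by 1.96 gives the last column.

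| ρ | β4 + β3 half-width, 2.1 as treatment | β4 + β3 half-width, 2.1 as baseline | Paired change half-width |
|---|---|---|---|
| 0.5 | 0.82 | 0.61 | 0.31 |
| 0.7 | 0.68 | 0.48 | 0.24 |
| 0.9 | 0.41 | 0.28 | 0.14 |

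These are different quantities: the paired change does not subtract the pre-treatment trend. It is, however, the alteration that the endpoint names, and it needs no baseline slope.

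**5. Time window**

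The objective is 12 months, but Stage 1 treatment runs to 24 months and optionally 36. SAP 4.4.2 sets no cut-off, so β3 may be fitted to data well beyond the stated window.

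**The case against.** This is a phase I/IIa trial sized by feasibility, with few films per child, so individual plots are a reasonable display. SAP 4.4.2 also opens by applying its model to secondary outcome measures in general. The plots should stay. But the operative sentence names six outcomes and none is a bone measure, so the general opening does not supply an estimate. Sparse films argue for a simpler estimate, not for none.

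A reader might infer that EQ-5D-Y is not analysed at all. The documents do not support that: Protocol 11.2.2 plans tables, utilities and comparison over time. The gap is that the SAP does not carry this forward. The health economics plan is for decision modelling and does not remove EQ-5D-Y from the trial's endpoints.

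A reader might also infer that the secondary objectives in general get no estimate. That is wrong for height, pain and PedsQL, which get β3 and β4 with robust intervals. The 12-month point estimate follows by addition, and opposite signs are information, not error. It is also fair to say that β4 + β3 is not change from baseline but departure from an extrapolated trend. What remains is the missing interval and the missing 12-month change.

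Finally, a reader might take "There is no randomisation or blinding in this trial" (SAP 2.3) to mean that the central radiologists see visit dates. That statement concerns the trial design and does not mention film reading. Protocol 8.7.8 has anonymised films labelled by study ID only, with angles measured centrally by at least two independent radiologists. Neither document says whether visit date or order is hidden, so no claim of unmasked reading can be made.

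**Conclusion.** The point holds in this form. One of four secondary objectives, bone conformation, has no planned estimate or interval. One of the two quality-of-life instruments, EQ-5D-Y, has no analysis in the SAP although the protocol promises one. Height z-score, pain and PedsQL have estimates but no 12-month contrast with an interval, and no 12-month cut-off.

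These findings rest on the text alone. The precision figures rest on an assumed ρ of 0.5 to 0.9, full recruitment and complete data; missing or merged visits would widen them. On those assumptions, leaving out the covariance is a small error on the questionnaire schedule (0.287 against 0.303 SD at ρ = 0.5). The absence of any bone estimate is the larger gap. The primary growth analysis is unaffected, so this should be corrected but does not threaten the main result.

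**What to change.** 1. **Bone.** For neck-shaft angle (left and right, clustered within child) and knee deviation, report the mean paired change from the start-of-treatment film (visit 1.1 in Stage 1, visit 2.1 in Stage 2) to 12 months, with a 95% CI. Give bone-age z-score the same treatment as supportive. Do not rely on the slope-plus-step model, because Stage 2 has only one earlier film. State which film counts as the 12-month film when a visit was combined or brought forward. Settle whether TW3 is an outcome. SAP 2.5 reads as if films are taken at every baseline visit, whereas Protocol Table 8 schedules only visit 1; reconcile the two.
2. **EQ-5D-Y.** Carry the Protocol 11.2.2 analysis into the SAP (tables, utilities, comparison across time points) and add change to 12 months with a 95% CI.
3. **Modelled outcomes.** Besides β3 and β4, report β4 + β3 × 1 year with a 95% CI by linear combination, labelled as departure from the baseline trend, and the mean change from baseline to 12 months. State whether data after 12 months of treatment enter this fit.

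The cost is a short SAP amendment, one post-estimation command per outcome and a few paired summaries; the data are already collected. Date the amendment before the secondary outcomes are analysed, or label the additions post hoc. A paired change in a single-arm trial includes natural growth, so show the change from visit 1 to the start-of-treatment film beside it.

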4.4.2 Statistical modelling

A more general version of the statistical model used for the analysis of the primary outcome will be used to assess changes in secondary outcome measures possibly related to treatment. The model additionally allows for a possible step change in response at the start of the treatment period.

Defining τ_{ij} , t_{ij} and T_i in the same manner as used for the primary outcome analysis, let y_{ij} denote a continuous response variable, the model for which is:

$$y_{ij} = \beta_1 + \beta_2 t_{ij} + \beta_3 \tau_{ij} (t_{ij} - T_i) + \beta_4 \tau_{ij} + \varepsilon_{ij},$$

where β_1 , β_2 , β_3 and β_4 are regression parameters to be estimated using Generalised Estimating Equations (GEE). The "working" correlation matrix is the same as used for the primary analysis.

- During the baseline period, $y_{ij} = \beta_1 + \beta_2 t_{ij} + \varepsilon_{ij}$.
- At the start of the treatment period, $y_{ij} = \beta_1 + \beta_2 T_i + \beta_4 + \varepsilon_{ij}$.
- During the treatment period, $y_{ij} = (\beta_1 \beta_3 T_i + \beta_4) + (\beta_2 + \beta_3)t_{ij} + \varepsilon_{ij}$.

The step change in response at the start of the treatment period is modelled by the parameter β_4 ; the parameter β_3 represents the increase in slope during the treatment period compared to the baseline period as previously.

Height *zscore*, PedsQL Pain Coping Inventory total score, Pediatric Pain Questionnaire VAS score, Paediatric Quality of Life Inventory (PedsQL) total score, PedsQL Psychosocial Health sub-domain score and PedsQL Physical Health sub-domain score will be analysed using the STATA commend **xtgee** to estimate the parameters of the regression model above. The parameter β_3 and β_4 will be reported together with 95% confidence interval. The Huber/White/sandwich estimator of variance will be used to obtain confidence intervals [in STATA: vce(robust)].

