**Patients who have planned surgery or planned osteotomy will not automatically be ineligible for the trial. Every potential participant with planned surgery or osteotomy will be assessed clinically on a case by case basis through discussion of the site PI^a, with the CI and/or the clinical members of the TMG during the screening process. NB: Please ensure that patients fulfil the full eligibility criteria prior to enrolling them on to the trial and ensure eligibility is re-assessed after the baseline observation period is complete, and before the participant begins treatment with CBZ. If a patient is deemed unsuitable at the end of the baseline observation period re-assessment time point, further reassessment of eligibility is possible if the Site PI^a and CI are in agreement that the exclusionary results are subject to change. In such cases, eligibility can be re-assessed within a 3 month period. If a patient meets any of the exclusion criteria after the 3 month reassessment period, they will be withdrawn from the study.

Protocol waivers will not be permitted for this trial. Enrolling a patient who does not meet the inclusion/exclusion criteria is considered a protocol waiver and is in breach of Regulation 29 (SI 2004/1031) of the Medicines for Human Use (Clinical Trials) Regulations 2004 and EU Clinical Trial Directive 2001.

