8.4 Screening

Following consent and prior to entry into the trial, all subjects will be screened to assess eligibility ensuring compliance with the trial inclusion and exclusion criteria (sections 7.1, 7.2). Eligibility must be assessed by a medically qualified doctor and this assessment must be documented in the participant's medical notes. A copy of the site eligibility checklist must be filed in the participant's medical notes. The eligibility checklist must also be completed in the trial MACRO database for those patients who enter the trial. Only personnel formally delegated by the Principal Investigator to assess eligibility may perform this task.

Eligibility will be assessed following consent before the participant enters the trial and re-assessed after the baseline observation period is complete before the participant begins treatment with CBZ, to confirm they are still eligible for the trial.

To confirm the participant is eligible to take part in the MCDS-Therapy trial the following assessments will be conducted: -

- Review of past medical history and diagnosis of MCDS, including review of available previous radiographic assessments
- Physical examination including height, weight and sitting height
- Blood samples will be obtained for full blood count, Plasma biochemistry including renal function, bone biochemistry, vitamin D and liver function (max 2 ml total). Samples will be processed at the trial site local laboratories following standard local laboratory procedures.
- Urine based pregnancy test

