Adverse event recording			X	X
Concomitant medications	X		X	X
Biomarker blood sample (UK participants only)***			x	x

--Informed consent is ongoing process, if a participant moves age groups during the trial, the age appropriate PIS will be provided, and the participant will be re-consented *All assessments to be performed as described in the protocol trial assessments section 8.7

**Screening visit 1 and 2 may coincide with baseline observation visit 1 and baseline observation visit 2 may coincide with treatment visit 2.1 (Table 9) for stage 2 participants.

*** A maximum of 2ml blood will be taken for exploratory biomarker analysis and a maximum of 2ml blood will be taken for the measurement of Bone markers (osteocalcine and CTX), if available at site.

Assessment*	Visit 2.1** 0 months (+/- 14 days)	Weekly Telephone call (as required)****	Visit 2.2 3 months (+/- 14 days)	Visit 2.3 6 months (+/- 14 days)	Visit 2.4 9 months (+/- 14 days) ∞	Visit 2.5 12 months (must be completed on/before 31/01/2024)
Eligibility check	X					
Physical examination	X		Х	Х	X	Х
Confirmation of eligibility	x					
Tanner stage	X		X	X	Х	Х
Growth measurements	X		x	X	Х	Х
X-rays (left wrist for bone age and long leg standing AP)	x			x		х
Laboratory safety assessments (including urine dipstick) %	x			x		x
Bone biochemistry %	X			Х		X
Pregnancy testing (potentially child bearing females only)	x		x	x	x	Х
EQ-5D-Y questionnaire	x		Х	Х	Х	Х
PEDSQL questionnaires (QoL Inventory, Pain coping Inventory & Pain Questionnaire)	x		x	x	x	Х
Dose Evaluation		X				
Drug prescription	X		X	Х	X≎	
Adverse event recording	X	X	X	Х	X	Х
Medication counselling	X	X	X	Х	X	Х
Concomitant medications	X	X	X	Х	X	Х
Biomarker blood sample (UK participants only)*****	x		x	x	x	х

Table 9 – Schedule of events - Stage 2, Treatment phase (UK, Europe & International sites)

* All assessments to be performed as described in the protocol trial assessments section 8.7

**Visit 2.1 may coincide with stage 2 baseline observation visit 2 (Table 8). If visit 2.1 does not coincide with baseline observational visit 2, it must be within 14 days of baseline observation visit 2

**** phone calls may be required, if patient is unable to tolerate 20mg/kg dose and requires dose titration

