4.3.1 Statistical model for growth

For subject *i* (*i* = 1,..,*N*), let τ_{ij} be a treatment indicator taking the value 0 for measurements observed during the baseline period and 1 for measurements observed during the treatment period; treatment for individual *i* starts at time T_i .

Let y_{ij} denote a continuous response variable (e.g., height), observed at measurement times t_{ij} (j = 1,.., n_i), the model for which is:

$$y_{ij} = \beta_1 + \beta_2 t_{ij} + \beta_3 \tau_{ij} (t_{ij} - T_i) + \varepsilon_{ij},$$

where β_1 , β_2 and β_3 are regression parameters to be estimated using Generalised Estimating Equations (GEE). The "working" correlation matrix is given by,

$$Corr(\varepsilon_{ij}, \varepsilon_{ij'}) = \begin{cases} 1 & if \ j = j' \\ \rho & otherwise \end{cases}$$

This is sometimes referred to as an exchangeable covariance model. The first observation on each individual, y_{i1} , takes place at time t_{i1} =0.

- During the baseline period, $y_{ij} = \beta_1 + \beta_2 t_{ij} + \varepsilon_{ij}$.
- At the start of the treatment period, $y_{ij} = \beta_1 + \beta_2 T_i + \varepsilon_{ij}$.
- During the treatment period, $y_{ij} = (\beta_1 \beta_3 T_i) + (\beta_2 + \beta_3)t_{ij} + \varepsilon_{ij}$.

The parameter β_3 represents the change in slope between the baseline and treatment periods, i.e., the change in growth velocity.

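### SAP 4.4.2 switches the treatment step on at the pre-dose month-0 visit; if those records are coded as treated, a prompt effect on pain or PedsQL is split between a shrunken step and a false slope

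*SAP*

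**What the plan says.** SAP 4.3.1 defines the treatment indicator τ as "taking the value 0 for measurements observed during the baseline period and 1 for measurements observed during the treatment period", with treatment for child i starting at T_i. SAP 4.4.2 reuses τ, t and T_i and adds a step term β4·τ: "The model additionally allows for a possible step change in response at the start of the treatment period". Its line for the start of the treatment period gives the mean as β1 + β2·T_i + β4. Both β3 and β4 are to be reported with 95% confidence intervals for height z-score, the two pain instruments and the PedsQL scores.

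Protocol 8.6 (Table 4) and SAP 2.5.1 list Stage 2 visit 2.1 as month 0 of the treatment phase, and Stage 1 visit 1.1 as time 0 of dose titration. Protocol Tables 6 and 9 mark growth, the PedsQL and pain questionnaires, confirmation of eligibility and drug prescription at that visit. Protocol 8.4 requires eligibility to be "re-assessed after the baseline observation period is complete before the participant begins treatment with CBZ", and section 7.2 says the same.

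The month-0 visit may be the same occasion as the last baseline visit. The Table 9 footnote for Stage 2 says "Visit 2.1 may coincide with stage 2 baseline observation visit 2 (Table 8", and otherwise: "If visit 2.1 does not coincide with baseline observational visit 2, it must be within 14 days of baseline observation visit 2". Table 6 has the parallel rule for Stage 1. The SAP does not say which value of τ a shared visit takes.

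**The concern.** The value at T_i is untreated, yet the SAP's start-of-treatment line gives it the full treatment step. A step term is meant to pick up a shift that appears soon after treatment begins. If the first point on the treatment line is an untreated one, that line is pulled down at its left end. The step is under-reported and a trend appears that did not occur.

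An early shift is not far-fetched on the documents' own account. Protocol section 3 describes carbamazepine as routinely used for neuropathic pain. Protocol 8.8 raises the dose weekly, so a child who tolerates each increase completes titration well before the first post-dose questionnaire at month 3. Because β3 and β4 are the two reported effects, both the size and the time course of a pain or quality-of-life response could be misdescribed to those planning a later controlled trial.

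**Working it through.** **Inputs.** From the documents: questionnaires at months 0, 3, 6, 9 and 12 of treatment (Tables 6 and 9; none at week 2); 11 Stage 1 and 29 Stage 2 children; Stage 1 treated for 24 months, optionally 36; Stage 2 baseline at 0 and 6 months; exchangeable working correlation ρ with no value given. The documents state no effect size, SD or bias figure for this model, so there is no figure of theirs to reproduce. Assumptions: a true step of 1 unit, complete by month 3, no underlying trend, noise-free data, Stage 1 baseline at 0, 6 and 12 months, and ρ of 0, 0.5 and 0.9.

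**Hand check, Stage 2, separate month-0 record with τ = 1.** β3 and β4 give the treatment period its own straight line.
- Months since T_i: 0, 3, 6, 9, 12, with mean 6. Responses: 0, 1, 1, 1, 1, with mean 0.8.
- Sum of squares: 36 + 9 + 0 + 9 + 36 = 90. Sum of products: −3 + 0 + 3 + 6 = 6.
- β3 = 6/90 = 0.0667 per month = 0.80 per year.
- β4 = 0.8 − 6 × 0.0667 = 0.40.
- Implied effect at 12 months: 0.40 + 0.80 = 1.20, against a true 1.00.

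These values are the same for every ρ tried. For n equally spaced treatment visits with the first pre-dose, the share of the step lost is 2(2n − 1)/[n(n + 1)]: 18/30 = 0.600 for n = 5, 34/90 = 0.378 for n = 9 and 50/182 = 0.275 for n = 13.

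**Pooled fit, 11 + 29 children (ranges over ρ).**

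| Visits used | Month-0 record | β4 | β3 per year |
|---|---|---|---|
| Both stages to 12 months | separate, or shared and entered once, τ = 1 | 0.40 | 0.80 |
| Stage 1 to 24 months | separate, τ = 1 | 0.56–0.60 | 0.46–0.54 |
| Stage 1 to 24 months | shared, once, τ = 1 | 0.64–0.67 | 0.58–0.64 |
| Stage 1 to 36 months | separate, τ = 1 | 0.68–0.70 | 0.24–0.30 |
| Stage 1 to 36 months | shared, once, τ = 1 | 0.73–0.75 | 0.33–0.37 |
| Any of these | shared, once, τ = 0 | 1.00 | 0 |

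Coding a separate month-0 record as τ = 0 also returns 1.00 and 0, because every record with τ = 1 then carries the full step. If half the children have separate visits (τ = 1) and half have shared visits kept as baseline, with Stage 1 to 36 months, β4 is about 0.82.

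**Other checks.**
- A purely linear effect starting at T_i is recovered exactly: β4 = 0 and β3 is correct.
- If visits 2.4 and 2.5 are combined, as Table 9 allows, at an assumed month 10, β4 in Stage 2 alone falls to 0.34.
- If shared visits are kept only as τ = 1, Stage 2 alone gives a design of rank 3 out of 4. The pooled design has rank 4.
- In the primary model the treatment term is τ(t − T_i), which is zero at T_i whatever τ is.

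**Price of the recode, Stage 2 alone, separate visits, independent errors.** The treatment line's intercept has variance factor 1/5 + 36/90 = 0.6 with the month-0 record, and 1/4 + 7.5²/45 = 1.5 without it. The baseline line at T_i gains a second record, so its factor falls from 1 to 1/2. The total goes from 1.6 to 2.0, a standard error ratio of √(2.0/1.6) = 1.12. In the pooled fit with both stages cut at 12 months, the increase is about 15–25% depending on ρ.

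**The case against.** The best defence is that τ = 1 is tied to measurements observed during the treatment period. A measurement made before the first dose could be read as outside that period, and the start-of-treatment line as merely the treatment line evaluated at T_i. That reading is open, and for a shared visit kept as baseline there is no bias. For a separate visit 2.1 it is the less natural reading, because both documents list that visit under the treatment phase.

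Several stronger inferences are tempting, and the documents do not support them.
- A reader might infer that every prompt effect loses 60%. That figure needs τ = 1 at month 0 and both stages cut at 12 months. The stated objective is over 12 months, but SAP 4.4.2 sets no such window and SAP 2.1 pools the Stage 1 children. Nor is 60% a strict ceiling, as the early combined final visit shows.
- A reader might infer that the effect is lost. It is redistributed: with 12-month windows the implied 12-month effect is overstated by 20%. The individual plots in SAP 4.4.1 would also help reveal a flat post-dose shift.
- A reader might infer that the model cannot be estimated when visits coincide. Stage 2 alone cannot separate β2 from β4, but the planned pooled model can, through the Stage 1 children.
- A reader might infer that height z-score is equally exposed. Height accrues gradually, so an immediate step there is unlikely.

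**Conclusion.** The concern holds in conditional form. SAP 4.4.2 places the step at T_i, the records at T_i are pre-dose, and shared visits have no stated coding. If month-0 records take τ = 1, a pain or PedsQL effect complete by month 3 and then flat is reported as 40% of its size plus a false slope of 0.8 of the step per year when 12 months of treatment visits are used. With Stage 1 visits to 24 or 36 months, β4 recovers about 56–75%. As an illustration on the 0–100 pain scale, a prompt 10-point fall would read as a 4-point fall followed by a further 8 points per year.

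The size rests on the assumed response shape. The proportions do not depend on how large the step is. This should be fixed, but it does not undermine the trial's main conclusion: these are secondary outcomes, and the question of further development rests on growth velocity, whose model is not affected.

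**What to change.** In SAP 4.4.2:
- Set τ_ij = 1 only for measurements taken after the first carbamazepine dose (t_ij > T_i).
- Code visit 1.1 (Stage 1) and visit 2.1 (Stage 2) as τ = 0.
- Enter a visit that serves as both the last baseline visit and month 0 once, with τ = 0.
- Correct the start-of-treatment line to β1 + β2·T_i for the pre-dose measurement.

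The recode must go by stage as well as visit number, because Stage 1 visit 2.1 is month 12 on treatment and stays τ = 1.

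The cost is one sentence and one recode, with no new data. The change is not entirely free: β4's standard error rises by about 15–25% when month-0 visits are separate and both stages are cut at 12 months. Otherwise there is little or no loss.
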